8.5 Safety

Safety variables are as follows: adverse events, the number of laboratory values that fall outside of pre-determined ranges (hematology, clinical chemistry and clinical urinalysis), changes in vital signs (blood pressure, heart rate, respiratory rate, temperature) and electrocardiogram (ECG).

Phase II Study of Perindopril and Regorafenib in mCRC (PARICCA)

All adverse events whether considered drug-related or not, will be reported with start/stop dates, action taken, whether treatment was discontinued, any corrective measures taken, and outcome. For all events, the relationship to treatment and the severity of the event will be determined by the Investigator, using the terms and definitions given in Section 5.1.

A Treatment-emergent adverse event is defined as any event arising or worsening after the start of study drug administration until 30 days after the last study medication

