5.1.1 Inclusion criteria

In order to be eligible, all inclusion criteria must be met.

A patient must:

- Understand, be willing to give consent, and sign a written informed consent form prior to undergoing any study-specific procedure
- Be male or female and ≥ 18 years of age
- Histological or cytological documentation of adenocarcinoma of the colon or rectum.
- Patients with metastatic colorectal cancer (Stage IV) previously treated with fluoropyrimidine-based chemotherapy, oxaliplatin, irinotecan, an anti-VEGF therapy, and, if *KRAS* wild type, an anti-EGFR therapy.

Phase II Study of Perindopril and Regorafenib in mCRC (PARICCA)

- Progression during or within 3 months following the last administration of approved standard therapies, or have experienced intolerance to previous therapy. Patients treated with oxaliplatin in an adjuvant setting should have progressed during or within 6 months of completion of adjuvant therapy. (Please note that in Canada patients are not re-challenged with oxaliplatin in the metastatic setting).
- Metastatic CRC patients with measurable or non-measurable disease
- Life expectancy of at least 3 months
- Have an Eastern Cooperative Oncology Group performance status of 0 or 1 (within 14 days prior to the initiation of study treatment)
- Have adequate bone marrow, liver function, and renal function as measured by the following laboratory assessments conducted within 7 days prior to the initiation of study treatment:
 - Total bilirubin \leq 1.5 times the upper limit of normal (ULN)
 - Alanine aminotransferase (ALT) and aspartate aminotransferase (AST) \leq 2.5 times the ULN ($<$ 5 times ULN for patients with liver involvement of their cancer)
 - Lipase \leq 1.5 times the ULN
 - Serum creatinine \leq 1.5 times the ULN
 - Glomerular filtration rate \geq 30 mL/min/1.73 m² according to the modified diet in renal disease abbreviated formula
 - International normalized ratio (INR) of prothrombin time (PT; PT-INR) and partial thromboplastin time (PTT) \leq 1.5 times the ULN
 - Platelet count \geq 100000 /mm³, hemoglobin (\geq 9 g/dL, absolute neutrophil count \geq 1500/mm³).
 - Alkaline phosphatase limit \leq 2.5 times the ULN ($<$ 5 times ULN for patients with liver involvement of their cancer)
- If female and of childbearing potential, have a NEGATIVE result on a pregnancy test performed a maximum of 7 days before initiation of study treatment

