AST and/or ALT baseline G0 → G1 or baseline G1 → G2	Treat on time and check AST, ALT and bilirubin 2x/week for 2 weeks followed by weekly assessments for at least 4 weeks.		Treat on time and check AST, ALT and bilirubin 2x/week for 2 weeks followed by weekly assessments for at least 4 weeks.
AST and/or ALT baseline G0 → G2	Delay until ≤ G1 and check AST, ALT, bilirubin 2x/week.	Reduce 1 dose level and check AST, ALT, bilirubin 2x/week for 2 weeks followed by weekly assessments for at least 4 weeks. ^a	Discontinue ^b
AST and/or ALT baseline any grade → G3	Delay until ≤ G1 if baseline was G0 or G1 OR until G2 if baseline was G2. Check AST, ALT, bilirubin 2x/week. If ALT or AST > 8 x ULN with a concomitant rise in bilirubin (of any degree) compared to previous bilirubin values, consider permanent discontinuation at the first occurrence ^b .	Reduce 1 dose level and check AST, ALT, bilirubin 2x/week for 2 weeks followed by weekly assessments for at least 4 weeks. ^a	Discontinue ^b
AST and/or ALT baseline any grade → G4	Discontinue ^b		

Abbreviations: AST = aspartate aminotransferase, ALT = alanine aminotransferase
 
^a If all values remain stable for 2 full cycles, dose re-escalation may be considered at the discretion of the investigator. After re-escalation AST, ALT, bilirubin should be checked 2x/week for 2 weeks, followed by weekly assessments for at least 4 weeks.
 
^b In case of discontinuation, check AST, ALT, bilirubin should be checked twice a week for 2 weeks, followed by weekly assessments until recovery to baseline.
			

During the first 2 cycles of treatment, ALT, AST and bilirubin must be monitored weekly.

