7.1.1 Tabulated overview

Table 7

Procedure	Day -28 to Day -1	Day -14 to Day -1	Day -7 to Day -1	Cycle 1				Cycle 2				Cycle 3+	End of treatment	Follow up (+1 month)
				Day1	Day7	Day14	Day21	Day1	Day7	Day14	Day21			
Medical History	x												x	
Physician Visit		x		x	x	x	x	x		x		x	x	
Concomitant Meds.		x		x	x	x	x	x	x	x		x	x	x
ECOG		x		x	x	x	x	x		x		x	x	
Blood Pressure		x		x	x	x	x	x	x	x		x	x	
Liver Function Tests			x	x	x	x	x	x		x		x	x	
12-lead ECG	x			x				x				x	x	
Cardiac Function Test*				x ¹				x ¹				x ¹		
Lipase Testing			x	x [#]				x				x	x	
PT or PT-INR and PTT			x	x [#]				x				x	x	
Full urinalysis, measure of proteinuria and GFR			x	x [#]				x				x	x	
AE				x	x	x	x	x	x	x		x	x	x
CEA			x	x [#]				x				x	x	
CBC			x	x [#]				x				x	x	
Creatinine			x	x [#]				x				x	x	
Electrolytes			x	x [#]				x				x	x	
TSH			x	x [#]				x				x	x	
Chemistry			x	x [#]				x				x	x	
hCG			x											
CT - every eight weeks	x			x								x		
Photos				x	x	x	x							

Lipase, Creatinine, Electrolytes are generally inclusive with chemistry.

34 patients, Study expected to last 2 -4 cycles

Tests will be administered as per standard of care for Regorafenib

PROTOCOL Version 2.2 Dated 08 February 2017

Phase II Study of Perindopril and Regorafenib in mCRC (PARICCA)

Weekly monitoring by physician in first cycle

* Echocardiogram or MUGA scan

¹ Echocardiogram or MUGA scan only if clinically indicated. Echocardiograms or MUGA scans should be performed by the same operator to minimize inter-observer variability.

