7.5 Safety

Although we are assuming that the co-administration of perindopril with regorafenib will mitigate HFSR symptoms, this may not be the case. Grade 3 HFSR rate will be evaluated after the first 10 patients have completed at least one cycle of regorafenib. If a significantly higher rate of grade 3 HFSR is seen in these first 10 patients i.e. Grade 3 is seen in more than 5 out of the 10 patients, the study will be discontinued.

Safety variables for **regorafenib** are as follows: adverse events, laboratory changes (hematology, clinical chemistry and clinical urinalysis), changes in vital signs (blood pressure, heart rate, respiratory rate, temperature) and electrocardiogram (ECG). These will be measured as per standard of care for regorafenib, as per study schedule (Table 7). See more details from product monograph below.

Phase II Study of Perindopril and Regorafenib in mCRC (PARICCA)

Safety variables for **perindopril** can be obtained from the COVERSYL® Product Monograph. The most frequent adverse reactions observed with perindopril are: cough, dizziness, headache, asthenia, gastro-intestinal disorders (abdominal pain, nausea, dyspepsia). The most serious adverse reactions are: hypersensitivity reaction (angioedema), renal dysfunction (in high risk patients), pancreatitis, blood disorders (pancytopenia, agranulocytosis, and thrombocytopenia). During the long-term safety assessment in heart failure patients, the severe adverse events occurring with the highest frequency were angina pectoris and orthostatic hypotension. The most severe drug reactions from post-marketing experience were pancreatitis and blood disorders (pancytopenia, agranulocytosis, and thrombocytopenia).

More detailed safety variables from the regorafenib monograph include:

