7.5.1.3 Assessments and documentation of adverse events

All adverse events occurring after the subject has signed the informed consent must be fully recorded in the subject's case record form.

Documentation must be supported by an entry in the subject's file. A laboratory test abnormality considered clinically relevant, e.g., causing the subject to withdraw from the study, requiring treatment or causing apparent clinical manifestations, or judged relevant by the investigator, should be reported as an adverse event. Each event should be described in detail along with start and stop dates, severity, relationship to investigational product, action taken and outcome.

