8.1 General considerations

Statistical analyses will be performed using SAS 9.3. Demographic and other baseline characteristics will be listed and summarized. Qualitative data will be summarized using frequencies and percentages and quantitative data will be summarized by appropriate descriptive statistics (mean, standard deviation, median, minimum and maximum). Secondary safety variables will be summarized using descriptive statistics and exploratory graphical presentations of the data.

Duration of study treatment exposure, cumulative dose and dose intensity will be summarized. The number of patients with dose changes/interruptions and withdrawals will be presented along with reasons for the dose change.

Variables related to tumor response and disease progression will be evaluated based on investigator assessed RECIST criteria, version 1.1. In cases where radiographic imaging is not possible, clinical progression may be used. Clinical progression is based on the judgment of the investigator.

Toxicity related variables will be evaluated using the CTCAE v4.03 criteria.

Biomarker and pharmacokinetics will not be performed in this study and no subgroup analysis will be performed.

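### Section 8.5 counts out-of-range laboratory values, with no patient unit, denominator or baseline, so the summary mixes toxicity with testing frequency and entry status

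*Combined protocol and SAP*

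**What the plan says.** Section 8.5 lists the safety variables. For laboratory data the variable is "the number of laboratory values that fall outside of pre-determined ranges (hematology, clinical chemistry and clinical urinalysis". Section 7.5 lists the same domain differently, as "adverse events, laboratory changes (hematology, clinical chemistry and clinical urinalysis), changes in vital signs", and does not define a change. Neither section gives the ranges, the unit of analysis, a denominator, a rule for repeat or unscheduled tests, or a comparison with baseline.

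Three nearby provisions come close but do not fill the gap:

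- Section 8.5 has a new-or-worse rule, but for adverse events only: "A Treatment-emergent adverse event is defined as any event arising or worsening after the start of study drug administration until 30 days".
- Section 8.1 says "Toxicity related variables will be evaluated using the CTCAE v4.03 criteria", and promises descriptive summaries of secondary safety variables. It does not tie grading to the laboratory count.
- Section 7.5.1.3 turns a laboratory finding into an adverse event when it is clinically relevant or the investigator judges it so: "A laboratory test abnormality considered clinically relevant, e.g., causing the subject to withdraw from the study, requiring treatment or causing apparent clinical manifestations".

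Section 8.2 defines a safety set of all dosed patients, which could serve as the denominator. Section 8.5 does not link it to the laboratory variable.

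**The concern.** A count of values treats each blood draw as an independent unit. That is harmless only if patients start normal, are tested equally often, and are not tested more because a result was abnormal. The protocol departs from all three conditions.

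- **Entry status.** Section 5.1.1 admits AST, ALT and alkaline phosphatase up to 2.5 x ULN, relaxed to below "5 times ULN for patients with liver involvement of their cancer". Bilirubin, lipase and creatinine may be up to 1.5 x ULN, and haemoglobin as low as 9 g/dL.
- **Unequal testing.** Liver tests are drawn more often than blood counts, and patients treated longer are drawn more often.
- **Outcome-dependent testing.** Table 6 intensifies testing after an AST or ALT rise: "Treat on time and check AST, ALT and bilirubin 2x/week for 2 weeks followed by weekly assessments for at least 4 weeks".

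Table 6 itself acts on the shift from each patient's baseline grade, whereas the analysis variable does not refer to baseline. At stake is the readability of the laboratory summary in an open-label, single-arm trial without a data monitoring committee (section 3.1). Sections 7.5 and 7.5.1.5 (Expected adverse events) name renal dysfunction, blood disorders and severe liver injury among the serious reactions to the two drugs. The laboratory table is the one view of these that does not pass through a judgement of clinical relevance.

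**Working it through.** The plan attaches no figure to this variable, so there is none to reproduce. The check counts scheduled draws and applies section 8.5 literally.

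**Inputs**

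- Treatment length, from the note to Table 7: "34 patients, Study expected to last 2 -4 cycles".
- Liver tests after first dose (Table 7): Cycle 1 Days 7, 14 and 21; Cycle 2 Days 1 and 14; Day 1 of each later cycle; end of treatment.
- CBC, creatinine, lipase and electrolytes after first dose (Table 7): Day 1 of Cycle 2 and of each later cycle; end of treatment.
- The line below Table 6: ALT, AST and bilirubin weekly during the first two cycles. This conflicts with section 7.1 and Table 7, so both are used.
- Table 6 after a rise: twice weekly for 2 weeks, then weekly for at least 4.
- Assumption: the unstated ranges are normal limits.

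Screening and Cycle 1 Day 1 values are left out, which favours the plan.

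**Step 1: a stable abnormality present at entry**

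| | Two cycles | Four cycles | Ratio |
|---|---|---|---|
| Liver test, e.g. alkaline phosphatase | 3 + 2 + 1 = 6 | 3 + 2 + 2 + 1 = 8 | 8/6 = 1.33 |
| CBC, creatinine, lipase, electrolytes | 1 + 1 = 2 | 3 + 1 = 4 | 4/2 = 2.0 |

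A patient whose result never changes adds 6 to 8 (or 2 to 4) to the count. The number of patients with a new or worse abnormality is 0. At the same per-draw risk, a liver analyte has 6/2 = 3 times (two cycles) or 8/4 = 2 times (four cycles) as many chances to be counted as a blood-count analyte. Dropping pre-dose values does not cure this, because the figures above already exclude them.

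Scaled to 34 patients, with a share b entering with one stable out-of-range liver analyte and nobody developing toxicity, the count is 34 x b x 6 over two cycles and 34 x b x 8 over four. The documents do not give b; the range is an assumption.

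| b | Two cycles | Four cycles | Patients new or worse |
|---|---|---|---|
| 10% | 20 | 27 | 0 |
| 30% | 61 | 82 | 0 |
| 50% | 102 | 136 | 0 |

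**Step 2: one AST rise**

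Take a rise first seen at Cycle 1 Day 14 that stays out of range for six weeks, with scheduled draws in that window coinciding with Table 6 draws. AST is used because the liver-test list in section 7.1 and the chemistry panels in 7.1.2.1 and 7.1.2.2 omit ALT.

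- Table 6: 1 triggering value + 2 x 2 + 4 x 1 = 9 (8 further draws at minimum).
- Table 7 only: Cycle 1 Days 14 and 21, Cycle 2 Days 1 and 14 = 4. Ratio 9/4 = 2.25.
- Weekly rule: Days 14, 21, 28, 35, 42, 49 and 56 = 7. Ratio 9/7 = 1.29.

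On a patient-level variable this episode counts once.

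**Step 3: dependence on the ranges**

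If the ranges were set at toxicity or alert limits above the entry limits, the Step 1 counts could fall to zero and a mild rise in Step 2 might not count at all. Values beyond such limits would still be counted once per draw.

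**The case against.** The strongest reply is that laboratory toxicity is captured elsewhere, and much of it stands. Section 7.5.1.1 includes abnormal laboratory findings among adverse events, treats conditions that begin or deteriorate after consent as events, and leaves unchanged ones as medical history. These events are graded by CTCAE v4.03. Section 7.5.3 adds regular review of Grade 4 laboratory abnormalities. What remains outside is the set of abnormalities that nobody judged clinically relevant, and for those the count is the only planned summary.

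Several stronger readings are tempting, and the documents do not support them.

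- *The count measures testing and entry status instead of toxicity.* New drug-related abnormalities also raise it, and Table 6's extra draws follow rises attributed to study drug. It is a mixture.
- *It undermines the secondary toxicity objective in 8.4.* That objective concerns CTCAE-graded toxicities, which sections 2.2 and 8.4 do not derive from this count.
- *It ranks a stable baseline abnormality above a Grade 4 event.* Section 8.5 defines no patient score, no pooling across analytes and no ordering.
- *Extra testing inflates an episode 2.25-fold.* That holds only against Table 7. Against the weekly rule it is about 1.3-fold.
- *Most counted values will be pre-existing.* The documents give no share of patients abnormal at entry and no rate of new abnormality, so no such proportion can be derived.

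The mention of a later statistical analysis plan in section 7.3 helps little. It sits under efficacy and promises a list of variables, while section 8.5 has already defined this one.

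**Conclusion.** The point holds in limited form. As written, the laboratory variable has no patient unit, denominator, baseline or stated ranges, and sections 7.5 and 8.5 describe it differently. Under the normal-limits assumption, a stable entry abnormality contributes 6 to 8 liver values or 2 to 4 blood-count values with no new toxicity. One six-week AST episode contributes 9, against 4 or 7 depending on which of the protocol's two liver schedules is followed. These draw counts rest on the protocol's tables; the 34-patient totals also rest on an assumed share of abnormal entrants.

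The consequence is a descriptive summary that is hard to interpret. The primary test against 47%, the sample size of 34 and the interim rule on Grade 3 HFSR are unaffected. It is worth correcting because section 8.5 states a specific method and a better one is available at little cost.

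**What to change.** In section 8.5, replace the count of values with the following:

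- For each laboratory parameter, the number and percentage of patients whose worst CTCAE v4.03 grade between first dose and 30 days after last dose is higher than their baseline grade. The denominator is safety-set patients with a baseline and at least one post-baseline value, and unscheduled results are included.
- A shift table of baseline grade against worst grade.
- For parameters without a CTCAE grade, such as some urinalysis items, normal-to-abnormal shifts against ranges that the plan states.

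Reword section 7.5 to match. Reconcile the liver-test schedule in section 7.1 and Table 7 with the weekly rule below Table 6, and the omission of ALT from the listed panels with its use in Table 6, so that the available values are clear.

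The cost is a short text change and a few more tables, largely from results the protocol already collects. One limitation remains: a worst grade still depends somewhat on the number of draws and time on treatment. The exposure summary already promised in section 8.1 should therefore be shown alongside.

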8.6 Planned interim analyses

A single interim analysis is planned to be performed at the point that 10 patients have completed their first cycle of study treatment. This will be to determine if the study should continue. The study will be discontinued if 5 out of the first 10 patients exhibit a Grade 3 HFSR. The lower bound limit of the 95% confidence interval would be 18.7% which is higher than the 17% of patients who experienced HFSR grade 3 severity in the CORRECT trial.

8.7 Determination of sample size

A sample size of 34 patients achieves 80% power to detect a 50% reduction in all grades of HFSR toxicity (from 47% as seen in the CORRECT trial to 24%) using the normal approximation to the binomial distribution and a 2-sided 5% significance level.

9. Data handling and quality assurance

9.1 Data recording

Designated investigator staff will enter the data required by the protocol in a specific study data collection tool. Designated investigator staff will not be given access until they have been trained. The data entered will be reviewed by investigational staff for completeness and accuracy and will provide instruction for any required corrections or additions to the data. Obvious errors will be corrected by the designated investigator data entry staff. Validation program checks for data discrepancies will allow the data to be confirmed and corrected before analysis.

9.2 Monitoring

In accordance with applicable regulations, GCP, and sponsor's procedures, monitors will contact the site prior to the start of the study to review with the site staff the protocol, study requirements, and their responsibilities to satisfy regulatory, ethical, and sponsor's requirements.

When reviewing data collection procedures, the discussion will also include identification and documentation of source data items.

Phase II Study of Perindopril and Regorafenib in mCRC (PARICCA)

The sponsor/designee will monitor the site activity to verify that the:

- Data are authentic, accurate and complete
- Safety and rights of subjects are being protected
- Study is conducted in accordance with the currently approved protocol (including study treatment being used in accordance with the protocol)
- Any other study agreements, GCP, and all applicable regulatory requirements are met.

The investigator and the head of the medical institution (where applicable) agrees to allow the monitor direct access to all relevant documents.

9.3 Data processing

Clinical data management will be performed in accordance with investigator's standards and data cleaning procedures. This is applicable for data recorded on CRF as well as for data from other sources (e.g. IVRS, laboratory, ECG).

For data coding (e.g. AEs, medication), internationally recognized and accepted dictionaries will be used.

9.4 Audit and inspection

To ensure compliance with GCP and regulatory requirements, a member of the sponsor's quality assurance unit may arrange to conduct an audit to assess the performance of the study at the study site and of the study documents originating there. The investigator/institution will be informed of the audit outcome.

In addition, inspections by regulatory health authority representatives and IEC(s)/IRB(s) are possible. The investigator should notify the sponsor immediately of any such inspection. The investigator/institution agrees to allow the auditor or inspector direct access to all relevant documents and allocate his/her time and the time of his/her staff to the auditor/inspector to discuss findings and any issues. Audits and inspections may occur at any time during or after completion of the study.

9.5 Archiving

Essential documents shall be archived safely and securely in such a way that ensures that they are readily available upon authorities' request.

Patient (hospital) files will be archived according to local regulations and in accordance with the maximum period of time permitted by the hospital, institution or private practice. Where the archiving procedures do not meet the minimum timelines required by the sponsor, alternative arrangements must be made to ensure the availability of the source documents for the required period.

Phase II Study of Perindopril and Regorafenib in mCRC (PARICCA)

The investigator/institution notifies the sponsor if the archival arrangements change (e.g. relocation or transfer of ownership). The investigator site file is not to be destroyed without the sponsor's approval.

The investigator's contract will contain all regulations relevant for the study center.

10. Premature termination of the study

The study will be discontinued if 5 of the first 10 patients exhibit a Grade 3 or higher HFSR. Note that in the CORRECT trial, 47% of patients experienced HFSR of all grades with 17% experiencing HFSR with grade 3 severity.

(Note: Given the small patient numbers (n=10) for the interim analysis and using the expected number from CORRECT, there would be ~2 expected with HFRS at Grade 3. If you have n≥3 to discontinue the study, that may be problematic given a single patient can have a significant impact at such low numbers. Increasing it to 5 would indicate there is a signal suggesting a ≥2 fold increase in grade 3 HFSR events and study should be discontinued.)

The sponsor/Investigator has the right to close this study at any time, which may be due but not limited to the following reasons:

- If risk-benefit ratio becomes unacceptable owing to, for example,
 - Safety findings from this study (e.g. SAEs)
 - Results of any interim analysis
 - Results of parallel clinical studies
 - Results of parallel animal studies (on e.g. toxicity, teratogenicity, carcinogenicity or reproduction toxicity).
- If the study conduct (e.g. recruitment rate; drop-out rate; data quality; protocol compliance) does not suggest a proper completion of the trial within a reasonable time frame.

For any of the above closures, the following applies:

- Closures should occur only after consultation between involved parties.
- All affected institutions (e.g. IEC(s)/IRB(s); competent authority (ies); study center; head of study center) must be informed as applicable according to local law.
- All study materials (except documentation that has to remain stored at site) must be retained as per BCCA regulations.

In case of study closure, ongoing subjects, including those in post study follow-up, must be taken care of in an ethical manner.

PROTOCOL Version 2.2 Dated 08 February 2017

Phase II Study of Perindopril and Regorafenib in mCRC (PARICCA)

Details for individual subject's withdrawal can be found in Section 5.2.1.

11. Ethical and legal aspects

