3.5 Location of laboratory and imaging facilities

[figure not shown]
The laboratory and imaging facilities for this study are both located on the 3rd floor of the BC Cancer Agency at [name].

4. Study design

Phase II, open-label, single-arm trial of patients with refractory mCRC treated with regorafenib (160 mg/day) and perindopril (4 mg/day).

This study will be conducted at the BC Cancer Agency (Vancouver Centre) only.

PARICCA trial design

Primary endpoint: Incidence of all grade toxicities for HFSR

Secondary endpoints: Incidence of (all grade) hypertension & toxicity; Severity of HFSR; Time course to development of worst grade (stage3) HFSR; Progression Free Survival.

Treat until progression, unacceptable toxicity, or withdrawal

During the study period, patients will undergo evaluations for safety and drug accountability every cycle. Drug safety will be monitored and evaluated continuously throughout the study, including a 30-day follow up period. Patients will continue on treatment until one of the following occurs (main criteria):

- Progressive Disease as defined by Response Evaluation Criteria in Solid Tumors (RECIST) criteria, version 1.1, or clinical progression
- Death
- Unacceptable toxicity
- Patient withdraws consent
- Treating physician determines discontinuation of treatment is in the patient's best interest
- Substantial non-compliance with the protocol

For the full list of criteria refer to section 5.2.1.

If in the Investigator's opinion, treatment with regorafenib is providing clinical benefit to a patient experiencing disease progression, the patient may continue treatment.

Justification of the design

47% of regorafenib treated patients in the CORRECT trial experienced HFSR of all grades, while 17% of regorafenib patients experienced grade 3 HFSR. All efforts need to be made to find new therapeutic combinations to reduce HFSR, as it causes a significant decrease in a patient's quality-of-life.

Although we are assuming that the co-administration of perindopril with regorafenib will mitigate HFSR symptoms, this may not be the case. If the HFSR is more severe with the addition of perindopril than with regorafenib alone, the study will be discontinued.

The choice of dosage and schedule to be used in this trial comes from data accumulated in previous phase III trials with regorafenib (CORRECT, CONCUR). The choice of dosage and schedule for perindopril is from the Coversyl monograph.

End of study

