8.3.2 Statistical hypothesis and method of analysis

The primary analysis will be a comparison of the proportion of patients with any grade HFSR toxicity to 47% using the normal approximation z-test statistic and 2-sided 5% significance level. The statistical hypotheses are

H0: $P = 0.47$ versus H1: $P \neq 0.47$

where P is the proportion of any grade HFSR toxicity.

The study includes a single interim safety analysis after 10 patients have completed the study medication.

The proportion of patients having worst grade 3 HFSR toxicity will be determined along with the 95% confidence interval.

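### The only quantified study-level HFSR stopping rule, one look at the first 10 patients, would stop the trial with probability of at most 23% if the true grade 3 rate were double the 17% reference

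*Combined protocol and SAP*

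**What the plan says.** Section 4 (justification of the design) states: "If the HFSR is more severe with the addition of perindopril than with regorafenib alone, the study will be discontinued". Section 1.5 says the same. Neither gives a number or a time.

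The number is in Section 8.6: "A single interim analysis is planned to be performed at the point that 10 patients have completed their first cycle of study treatment", with the trigger "The study will be discontinued if 5 out of the first 10 patients exhibit a Grade 3 HFSR". Its support is a confidence limit: "The lower bound limit of the 95% confidence interval would be 18.7% which is higher than the 17" per cent reported for grade 3 in CORRECT. Section 10 repeats the trigger for grade 3 or higher, as does the synopsis. It adds that about 2 events would be expected, that a trigger of 3 would let one patient weigh too heavily, and: "Increasing it to 5 would indicate there is a signal suggesting a ≥2 fold increase in grade 3 HFSR events".

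Other sections differ:
- **Threshold.** Section 7.5 requires more than 5 of 10.
- **Timing.** Section 7.5 says "Grade 3 HFSR rate will be evaluated after the first 10 patients have completed at least one cycle of regorafenib". Section 8.3.2 says "The study includes a single interim safety analysis after 10 patients have completed the study medication".

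No stopping probability is given for any true rate. No later HFSR look is planned, and Section 3.1 provides for no data monitoring committee.

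**The concern.** HFSR is both the primary endpoint and the toxicity that could be made worse. The text commits to stopping if it is worse, and the note in Section 10 links the trigger to a 2-fold increase. A reader such as an ethics board could take the two together to mean that a doubling of grade 3 HFSR would probably stop the trial. With 10 patients and one look, that needs checking. If it is not so, a trial in which perindopril doubles severe HFSR would most likely enrol all 34 patients without its one numeric safety rule being triggered.

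**Working it through.** **Inputs.** n = 10, one look (8.6). Trigger r = 5, read as 5 or more (8.6, 10, synopsis), or r = 6 (7.5). Reference grade 3 rate 17% (10). A doubling is 2 × 0.17 = 0.34; a tripling is 3 × 0.17 = 0.51. Planned total 34 (8.7).

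**1. The plan's own figures.** The exact (Clopper-Pearson) two-sided 95% interval for 5/10 is 18.7% to 81.3%, so the stated 18.7% reproduces. The expected count is 10 × 0.17 = 1.7, which matches the stated value of about 2. An observed 5/10 is 0.50/0.17 = 2.9 times the reference, while its lower limit is 0.187/0.17 = 1.1 times. A result of 5/10 therefore supports a rate above 17%, but does not by itself establish a doubling.

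**2. Stopping probability.** P(stop) = Σ C(10,k) p^k (1−p)^(10−k), summed from k = r to 10.

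| True grade 3 rate | 5 or more of 10 | More than 5 of 10 |
|---|---|---|
| 17% (no increase) | 1.7% | 0.3% |
| 34% (2-fold) | 22.7% | 8.4% |
| 42.5% (2.5-fold) | 43.1% | 21.1% |
| 51% (3-fold) | 64.7% | 40.2% |

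A doubling is missed in 77% of trials at r = 5 and in 92% at r = 6. Reading the trigger literally as exactly 5 gives 14.3% at 34%, so 23% is the ceiling on any reading. Solving P(stop) = 0.80 for p gives about 58% at r = 5 (3.4-fold) and 67% at r = 6 (4.0-fold).

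**3. Events after the look (conditional).** Suppose a fraction f of grade 3 events has occurred by the look, and replace p by f × 0.34. With f = 0.8, p = 0.272 and P(5 or more) = 10.6%. With f = 0.6, p = 0.204 and P = 3.6%. Both fractions are assumptions; the documents give none.

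**4. Patients outside the rule.** 34 − 10 = 24.

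**5. Re-applying Section 8.6's criterion (exact 95% lower limit above 17%).** The smallest counts that meet it are 5/10 (18.7%; 4/10 gives 12.2%), 8/20 (19.1%; 7/20 gives 15.4%) and 10/30 (17.3%; 9/30 gives 14.7%). With X events in the first 10 patients and Y in the next 10, the probability of stopping by 20 patients is P(X ≥ 5) + Σ P(X = x) P(Y ≥ 8 − x), summed over x = 0 to 4. The look at 30 is added in the same way. With full capture:

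| True rate | Look at 10 only | Looks at 10 and 20 | Looks at 10, 20 and 30 |
|---|---|---|---|
| 17% | 1.7% | 2.5% | 3.8% |
| 34% | 22.7% | 40.9% | 63.3% |
| 51% | 64.7% | 90.1% | 98.6% |

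If Section 7.5's threshold applied at the first look, the 10-and-20 figure at 34% would be 36.9%.

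**The case against.** **Section 10 claims no power.** A reader might infer that the design lacks a property the protocol asserts. The text does not support that: the note says what an observed 5 of 10 would suggest, which is a different statement from the chance of observing it under a true doubling. The two statements do not contradict each other. What stands is that the note is the stated reason for choosing 5, and that the chance is nowhere reported.

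**The trade-off was considered.** Section 10 explains why a lower trigger was avoided. Some preference for specificity in a 34-patient, single-centre phase II trial is legitimate. This does not explain why there is only one look.

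**Cycle 1 versus whole treatment.** It is tempting to say that 17% is a whole-treatment rate while the look counts only cycle 1 events, so that true sensitivity must be below 23%. The documents do not say so. The 17% is quoted without an observation window. No section limits the count to cycle 1 events; Section 7.5 says at least one cycle and Section 8.3.2 says completed medication. The loss in step 3 is therefore conditional.

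**Other protection exists.** A reader might infer that patients 11 to 34 have no HFSR protection. They do: the patient-level HFSR rules in Table 4, continuous safety monitoring (Section 4) and discretionary closure (Section 10). None of these sets a numeric study-level HFSR criterion.

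**The gain from more looks can be oversold.** The 63% is an upper figure. It assumes full capture, and about 22 of its points come from a look when at most 4 of 34 planned patients remain. Applying 80% or 60% capture to all three looks lowers it to 33% or 9.5%. That is pessimistic if all follow-up is counted, but it is the like-for-like comparison with step 3.

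**Conclusion.** The concern holds as a statement about sensitivity and disclosure. With a trigger of 5 of 10, the only quantified study-level HFSR rule stops the trial with probability 22.7% at a doubled grade 3 rate, and 8.4% under Section 7.5. It becomes reliable (80%) only at about a 3.4-fold increase. The commitment in Sections 1.5 and 4 is therefore much broader than the numeric rule behind it.

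These figures assume independent patients, the protocol's 17% reference, and every grade 3 event observed by the look. Incomplete observation would lower them. The primary analysis is unaffected.

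**What to change.** 1. **Reconcile first.** Sections 7.5, 8.3.2, 8.6, 10 and the synopsis must agree on the threshold (5 versus more than 5; grade 3 versus grade 3 or higher) and on when the look takes place. Which version is intended is for the sponsor to settle.

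2. **State the operating characteristics.** In Sections 8.6 and 10, give the stopping probabilities at true rates of 17%, 34% and 51% for the reconciled rule, beside the note on a 2-fold signal. Rewording that note alone would not be enough.

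3. **Add a later look.** In Section 8.6, re-apply the criterion already used there to all treated patients cumulatively, counting all follow-up to date. The main gain per patient still to be enrolled is at about 20 patients. A look at 30 is optional, since few planned patients remain. Say whether accrual pauses for the look.

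**Cost.** Wording, plus one or two tabulations of adverse event data already collected at scheduled visits. The false-stop probability at a true 17% rises from 1.7% to 2.5% with a look at 20, or to 3.8% with looks at 20 and 30. It is higher if the background rate here exceeds 17%: at an assumed 20%, the same formulas give 3.3% for the single look and 5.2% with a look at 20.
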